Physical examination, vital signs, weight	X	X ¹	X	X	X	X		X		X	X	
ECOG performance status	X	X ¹	X	X	X	X		X		X	X	
Skeletal survey ²	X											
Bone marrow ³	X	X ¹				X						
ECG	X											
CBC with differential	X	X ¹	X	X	X	X	X	X	X	X	X	
Research blood sample (10mL EDTA, 10mL Heparin)	X	X	X	X	X	X		X				
Calculated creatinine clearance (by Cockcroft-Gault) ⁴	X	X ¹				X ⁴		X ⁴		X ⁴		
TSH ⁵	X ⁵	X ¹						X ⁵		X ⁵	X ⁵	
SPEP w m-spike, 24hr urine w m-spike, serum and urine immunofixation, serum quantitative immunoglobulins, serum free light chain assay, beta-2 microglobulin,	X	X ¹				X		X		X	X	
Complete metabolic panel	X	X ¹	X	X	X	X	X	X	X	X	X	
LDH, phosphorus, uric acid	X	X ¹										
Pregnancy testing ⁷	X ⁸	X ⁸	X ⁸	X ⁸	X ⁸	X ⁸		X ⁸		X ⁸	X ⁸	
Register patient into RevAssist® program ⁹	X ⁹											
Prescribe lenalidomide via RevAssist® ¹⁰		X ¹⁰				X ¹⁰		X ¹⁰		X ¹⁰		
Azacitidine administration		X ¹¹										
Dexamethasone prescription		X ¹²				X ¹²		X ¹²				
Response assessment ¹³						X		X		X	X	
Record adverse events ¹⁴		X	X	X	X			X		X	X ¹⁴	
Record concomitant therapies/procedures	X	X				X		X		X	X	
Obtain Follow-Up anti-cancer treatments												X
Obtain Follow-Up survival information												X

* Variations of ± 3 days of the scheduled visit are permitted.

If Physical examination, vital signs, weight and ECOG performance status were done within 7 days of Day 1, they do not need to be repeated at Study Day 1. An unscheduled visit can occur at any time during the study. Source must be maintained for these unscheduled visits. The date for the visit and any data generated must be recorded on the appropriate CRF. Source documents for these unscheduled visits must also be maintained.

Version: 07/16/2015

¹ If screening assessments were done within 7 days of Day 1, they do not need to be repeated at Study Day 1.

² A skeletal survey may be obtained up to 28 days before day 1, cycle 1. It will be repeated every 12 months or earlier if symptoms suggest bony progression.

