4.2 Endpoints

4.2.1 Primary Endpoint

- The highest tolerated low dose (HTLD and HTLD-CKD for GFR > 60 ml/min and 30-59ml/min, respectively) of azacitidine in combination with GFR-adjusted lenalidomide will be defined as the highest dose level studied (up to 50mg/m² twice a week) at which dose limiting toxicity (DLT) occurs during the first 28-day cycle in ≤ 1 out of 6 patients. If one out of the first 3 patients with GFR ≥ 60 ml/min develops DLT, up to three additional patients are treated at the same dose level. In patients with GFR 30-59ml/min each dose level will enroll 6 patients unless more than 1 patient develops DLT.. Any dose level evaluated as the possible HTLD / HTLD-CKD must include 6 patients assessed for DLT. DLT is defined in Section 5.1. Toxicity according to CTCAE v.4.0 will be assessed with weekly CBC w. Diff and CMP during the first 6 cycles, then before each cycle, weekly history and physical during the first 28-day cycle, then before each cycle until cycle 12.

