5.1 Overall Design

This phase I/II trial will use a classical 3x3 design to determine the highest tolerated low dose (HTLD) for patients with GFR $\geq 60 \text{ ml/min}$ (Cockroft-Gault) and a modified 3x3 design to identify the highest tolerated low dose for patients with GFR 30-59 ml/min (HTLD-CKD) with additional enrollment of 10 patients at the highest tolerated low doses (HTLD / HTLD-CKD) of azacitidine.

Dose levels are outlined under 5.6.2.3.

Dose limiting toxicity (DLT) is defined as one of the following drug-related toxicities occurring during the first 28-day cycle (if a DLT is attributed to progressive disease, it will not be counted as a DLT):

- Any CTCAE v.4.0 grade ≥ 3 non hematologic toxicity (including febrile neutropenia)
 - For nausea, vomiting, or diarrhea, subjects must have a Grade 3 or 4 event that persists at this level despite the use of optimal symptomatic treatment, in order for these events to be considered a DLT

- Grade 4 transaminitis (serum transaminase $> 20 \times$ upper limit of normal [ULN]) is a DLT, while Grade 3 transaminitis (serum transaminase $> 5 \times$ and $\leq 20 \times$ ULN) must be present for ≥ 7 days to be considered a DLT
- Grade 3 or 4 venous thromboembolic events are not considered to be DLTs as long as anticoagulant therapy can be administered (see Section 6.5.3 and 6.6.2)
- Grade 3 or 4 hypokalemia, hypophosphatemia, hypomagnesemia or hyponatremia that responds to electrolyte supplementation within 7 days would not qualify as a DLT.
- CTCAE v.4.0 grade ≥ 4 neutropenia or thrombocytopenia that does not resolve to grade ≤ 3 within seven days of holding azacitidine and lenalidomide. While platelet transfusions are allowed at the discretion of the treating physician to maintain 100% dose level, any grade ≥ 4 thrombocytopenia that is followed by platelet transfusion prior to resolution to grade ≤ 3 will be counted as DLT.

Dose escalation for patients with GFR $\geq 60\text{ml/min}$:

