5.1.1.13 Adverse Events in Clinical Trials

In addition to hematologic toxicities the most frequent side effects and discomforts reported for azacitidine are nausea, vomiting and diarrhea. Infrequent side effects include neuromuscular aches, liver enzyme abnormalities, and renal tubular acidosis (the kidneys excrete too much bicarbonate and/or not enough hydrogen ions).

The azacitidine injection may result in redness and inflammation at the injection site.

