10.2 Datasets to be Analyzed

10.2.1 Dose Limiting Toxicity

Dose limiting toxicity is defined as any one of the following drug-related toxicities occurring during the first 28-day cycle (if a DLT is attributed to progressive disease, it will not be counted as a DLT):

- Any CTCAE v.4.0 grade ≥ 3 non hematologic toxicity (including febrile neutropenia)
 - For nausea, vomiting, or diarrhea, subjects must have a Grade 3 or 4 event that persists at this level despite the use of optimal symptomatic treatment, in order for these events to be considered a DLT
 - Grade 4 transaminitis (serum transaminase $> 20 \times$ upper limit of normal [ULN]) is a DLT, while Grade 3 transaminitis (serum transaminase $> 5 \times$ and $\leq 20 \times$ ULN) must be present for ≥ 7 days to be considered a DLT
 - Grade 3 or 4 venous thromboembolic events are not considered to be DLTs as long as anticoagulant therapy can be administered (see Section 6.5.3 and 6.6.2)

- Grade 3 or 4 hypokalemia, hypophosphatemia, hypomagnesemia or hyponatremia that responds to electrolyte supplementation within 7 days would not qualify as a DLT.
- CTCAE v.4.0 grade ≥ 4 neutropenia or thrombocytopenia that does not resolve to grade ≤ 3 within seven days of holding azacitidine and lenalidomide

Dose limiting toxicity will be assessed weekly during the first cycle. The highest tolerated low dose will be determined as described in Section 5.1.

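### Unresolved grade 3-4 hypophosphatemia and hypomagnesemia count as DLTs, but the cycle 1 schedule does not systematically measure either, so DLTs can be under-counted

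*Combined protocol and SAP*

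**What the plan says.** Section 5.1 defines DLT as one of several "drug-related toxicities occurring during the first 28-day cycle". Its general rule covers drug-related non-hematologic toxicity of grade 3 or higher. One exception reads: "Grade 3 or 4 hypokalemia, hypophosphatemia, hypomagnesemia or hyponatremia that responds to electrolyte supplementation within 7 days would not qualify as a DLT". Sections 6.2.1 and 10.2.1 repeat both the rule and the exception. A grade 3-4 fall in phosphorus or magnesium that does not respond in that time is therefore a DLT.

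On timing, Section 10.2.1 states: "Dose limiting toxicity will be assessed weekly during the first cycle". On laboratory tests, Section 4.2.1 states: "Toxicity according to CTCAE v.4.0 will be assessed with weekly CBC w. Diff and CMP during the first 6 cycles". The synopsis endpoint names the same two tests.

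In the Section 2 schedule, the row "LDH, phosphorus, uric acid" is marked at screening and at cycle 1 day 1 only. Footnote 1 lets the day 1 test be skipped if screening fell within the previous 7 days. Magnesium has no row and no footnote. The complete metabolic panel is marked weekly throughout cycle 1, but the documents do not list its analytes.

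Under Section 4.2.1, the HTLD or HTLD-CKD is the highest level studied with a DLT in no more than 1 of 6 patients.

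**The concern.** The primary endpoint is a count of DLTs, and part of the DLT definition rests on two laboratory values that the schedule does not call for once dosing has begun. A site that follows the schedule exactly may see neither the onset of such an event nor its response to supplementation.

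The decision rule leaves little room for error. With at most 1 DLT in 6 allowed, one unseen event at a level that already has one recorded DLT turns a fail into a pass. Under-ascertainment can only lower the count, so any error favors a higher declared dose. If testing depends on individual judgment, the count may also differ between the two institutions for reasons unrelated to dose.

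**Working it through.** **1. Definition against schedule.** Scheduled measurements after dosing starts, at days 8, 15 and 22 of cycle 1 and at cycle 2 day 1 (the end-of-cycle value):

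| Test | Scheduled time points | Pre-dose value |
|---|---|---|
| Complete metabolic panel | 4 of 4 | screening, waivable day 1 |
| Phosphorus, named | 0 of 4 | screening, waivable day 1 |
| Magnesium, named | 0 of 4 | none |

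**2. Does the weekly panel fill the gap?** The documents do not define it. Phosphorus has its own row, which suggests that the panel does not supply it. Nothing similar can be said for magnesium; its absence from the panel is an assumption.

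**3. The 7-day clause.** No repeat measurement of either analyte is scheduled. Weekly sampling alone would not fully solve this, because Section 2 allows each visit to move by 3 days. A day 8 visit held on day 5 and a day 15 visit held on day 18 are 13 days apart.

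**4. Effect on the decision rule.** The plan gives no figure to reproduce and no event rate, so this is an illustration on assumed rates. Let *b* be the per-patient probability of any other DLT and *e* that of a non-responding phosphorus or magnesium event. Assume the two are independent and every electrolyte event is missed.

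- True DLT probability: p = 1 − (1 − b)(1 − e)
- Probability that a level passes: P(≤1 of 6) = (1 − p)^6 + 6p(1 − p)^5

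Take b = 0.17, close to the one in six that the synopsis reports at 40 mg/m² twice a week.

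- As observed (p = 0.17): 0.83^6 + 6 × 0.17 × 0.83^5 = 0.327 + 0.402 = 0.729.
- True, with e = 0.05: p = 1 − 0.83 × 0.95 = 0.2115, which gives 0.240 + 0.387 = 0.627.

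Over a range of both rates:

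| Other DLTs (b) | Observed pass probability | True, e = 1% | True, e = 2% | True, e = 5% | True, e = 10% |
|---|---|---|---|---|---|
| 10% | 0.886 | 0.868 | 0.849 | 0.788 | 0.680 |
| 17% | 0.729 | 0.709 | 0.688 | 0.627 | 0.527 |
| 33% | 0.358 | 0.345 | 0.332 | 0.294 | 0.238 |

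The pass probability is overstated by about 1 to 2 percentage points at e = 1%, 6 to 10 at e = 5%, and 12 to 21 at e = 10%. If some events are found by unscheduled testing, the overstatement is smaller.

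**The case against.** The schedule is a minimum. Section 2 allows unscheduled visits at any time and requires their data to be recorded. Section 6.2 requires every abnormal laboratory result to be appraised. Cycle 1 also has a weekly history, physical examination and adverse event review. A reader might infer from the schedule that these DLTs cannot be detected at all; the documents do not support that, because prompted testing is open to the investigator. What remains is that appraisal applies only to tests that were done, and nothing in the plan prompts these two.

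The event is also narrow. It must be drug-related, grade 3 or 4, within 28 days and unresponsive to supplementation for 7 days. The adverse-effect lists for the three drugs name neither abnormality. The rate may well be low, so the 1% and 2% columns deserve as much attention as the larger ones.

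A reader might also infer a specific drug mechanism, because Section 5.1.1.13 mentions "liver enzyme abnormalities, and renal tubular acidosis" for azacitidine. That section lists these effects as infrequent and explains the tubular disorder through bicarbonate and hydrogen ions, which have their own monitoring and rules in Sections 5.7.4 and 5.7.5. Extending it to phosphate or magnesium loss goes beyond the text. So does describing the GFR 30-59 ml/min cohort as having myeloma kidney disease, since it is defined by GFR alone.

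**Conclusion.** The mismatch stands. Two of the four electrolytes named in the exception can produce a DLT, yet neither is systematically ascertained in cycle 1 after dosing starts. For phosphorus this follows from the schedule and its separate row. For magnesium it also rests on the assumption that the undefined panel omits it. The potential error runs in one direction: the declared HTLD or HTLD-CKD is unchanged or higher, never lower.

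Its size cannot be derived from the documents. On the assumptions shown, it ranges from 1 or 2 percentage points of pass probability if such events are rare to 10 or more if they affect 5 to 10% of patients; no passage supports the higher rates. Nothing in the documents shows that an event was missed at any completed level. This is a cheap improvement to how the primary endpoint is measured, not a defect that invalidates the design.

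**What to change.** - In the Section 2 table, add phosphorus and magnesium at cycle 1 days 8, 15 and 22 and at cycle 2 day 1, with a baseline magnesium, on the chemistry draw already scheduled.
- Schedule a repeat measurement after any grade 3-4 value, timed so that the existing 7-day clause can be judged despite the 3-day visit window.
- In the synopsis endpoint and Section 4.2.1, name both analytes beside "weekly CBC w. Diff and CMP during the first 6 cycles", limited to the cycle 1 time points above, and list what the complete metabolic panel contains.

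If the sponsor prefers not to add the tests, the minimum is to define the panel and state in Section 10.2.1 that these two DLTs rest on clinically prompted testing. That would make the text consistent but leave the under-count in place.

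The cost is two analytes on blood already drawn, with no added scheduled visit apart from an occasional repeat sample. The downside is slightly more laboratory expense and possibly an occasional additional DLT.

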- Promoter demethylation and gene reactivation will be measured at least at the HTLD / HTLD-CKD level using the Illumina® HumanMethylation27 BeadChip array on CD138 purified and CD34 purified cells obtained from bone marrow aspirates within 7 days before treatment start and at the end of cycle #1. RNA will be harvested from the same cell populations to confirm reactivation of selected genes identified on the array. Since the HTLD / HTLD-CKD is identified retrospectively DNA and RNA will be isolated from purified cell populations from all bone marrow aspirations before and after cycle #1.
- The RNA harvested from myeloma cells before and after the first cycle of therapy at the HTLD / HTLD-CKD level will furthermore be used to identify changes in global gene expression using the Illumina® HT12 array.

STUDY DURATION: 24 months	TOTAL SAMPLE SIZE: up to 44 patients
----------------------------------	---

DRUG SUPPLIES:

For study participants, Celgene Corporation will provide lenalidomide at no charge through the RevAssist® program and azacitidine, also at no cost, via the Cleveland Clinic Taussig Cancer Center chemotherapy pharmacy or the pharmacy of the University Hospital Seidman Cancer Center.

DOSING REGIMEN(S):

Combination therapy (six 28-day cycles)

GFR $\geq 60\text{ml}/\text{min}$ (initial study cohort):

All dose levels (**during phase I portion of the study**):

- Lenalidomide 25mg p.o. d1-21 every 28 d
- Dexamethasone 40mg p.o. weekly

Azacitidine dose levels:

1. 30mg/ m^2 s.c. weekly
2. 40mg/ m^2 s.c. weekly

3. 30mg/m² s.c. twice a week
4. 40mg/m² s.c. twice a week
5. 50mg/m² s.c. twice a week

GFR 30-59 ml/min (amendment 7):

All dose levels (**during phase I portion of the study**):

- Lenalidomide 10mg p.o. d1-21 every 28 d
- Dexamethasone 40mg p.o. weekly

Azacitidine dose levels:

CKD -1. 30mg/m² s.c. twice a week

CKD 1. 40mg/m² s.c. twice a week

CKD 2. 50mg/m² s.c. twice a week

Maintenance therapy (

Lenalidomide at last tolerated dose until disease progression.

2 Schedule of Study Assessments *

Procedure	Screening ≤ 7 days before day 1, cycle 1, unless indicated otherwise	Cycle 1				Cycle 2		Cycle 3,4,5,6		Maintenance Monthly during first 6 cycles, then every 2 months	Discontinuation From Protocol Therapy	Follow-Up Phase Every 3 months for 3 years from entry
		Day 1	Day 8	Day 15	Day 22	Day 1	Weekly	Day 1	Weekly			
Record prior medications, treatments	X											
Record prior anti-cancer therapies	X											

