5.10 Follow-Up

Subjects who discontinue treatment for any reason, will be followed every 3 months for 3 years from study entry (if patients are no longer treated at this Institution attempts will be made to obtain information over the phone as per Schedule of Assessments, Section 2). Patients, who stay on protocol therapy will be followed at least every 2 months according to schedule of study assessments (2) for 3 years from study entry. At treatment discontinuation, off study evaluations per the Schedule of Assessments, Section 2, will be done. In addition, subjects will undergo a safety assessment approximately 28 days post the last dose of protocol therapy.

6 Adverse Events

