10.2.4 Progression-free Survival

Progression-free survival will be calculated from the time of enrollment until the development of progressive disease or death from any cause, whichever occurs first. Patients who elect to undergo high dose chemotherapy followed by autologous stem cell transplantation will not be included in an analysis of progression-free survival.

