10.3 Statistical Methodology

The Kaplan-Meier method will be used to report progression free survival and overall survival for patients treated at the HTLD / HTLD-CKD and for the entire study cohort but excluding patients who elect to undergo high dose chemotherapy and autologous stem cell transplantation. For statistical methods pertaining to pharmacodynamic analyses please see under correlative science (5.5).

11 Regulatory Considerations

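### Progression is not collected after treatment stops and no censoring rule is given, so PFS cannot be determined as defined for patients who stop without progressive disease

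*Combined protocol and SAP*

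**What the plan says.** - **Follow-up content.** The last column of the Section 2 schedule is headed "Follow-Up Phase Every 3 months for 3 years from entry". Only two rows are marked in it: "Obtain Follow-Up anti-cancer treatments" and "Obtain Follow-Up survival information". The response assessment row and the row for serum and urine M-protein and free light chains are last marked at discontinuation from protocol therapy.
- **Who enters it.** Section 5.10: "Subjects who discontinue treatment for any reason, will be followed every 3 months for 3 years from study entry". For patients treated elsewhere, "attempts will be made to obtain information over the phone as per Schedule of Assessments, Section 2". This points back to the same schedule. Section 5.4 adds only a minimum contact frequency.
- **Endpoint.** Section 10.2.4: "Progression-free survival will be calculated from the time of enrollment until the development of progressive disease or death from any cause, whichever occurs first". Section 4.2.2 and the synopsis agree.
- **Estimator.** Section 10.3: "The Kaplan-Meier method will be used to report progression free survival and overall survival", for the HTLD / HTLD-CKD group and for the whole cohort. Transplant patients are excluded. No section gives a censoring date or says how new therapy is handled.
- **Stopping without PD.** Section 5.9 lists several routes, among them adverse events, a cycle delay of more than 21 days, permanent loss of lenalidomide and withdrawal of consent.
- **Confirmation.** Section 5.9.1 requires PD to be confirmed on two consecutive assessments.

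**The concern.** The definition needs the date of the first of two events, but after treatment stops the schedule collects only one of them. A death during follow-up is recorded. A progression before that death is not, unless someone happens to note it. Two analysts with the same database could draw different PFS curves and both be within the text: one by letting follow-up deaths and contact dates into the calculation, the other by censoring at the discontinuation visit.

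The trial is meant to give an initial impression of efficacy before a larger phase II study. Section 10.2.3 puts 16-22 patients at the HTLD / HTLD-CKD, so a few such patients can move that curve. A progression date that was not recorded at the time may be hard to recover later.

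**Working it through.** **1. Design figure.** The only design number is the maximum sample size. It reproduces: 18 started + (6 − 2) to complete dose level 5 + 2 × 6 CKD + 10 extension = 44. There is no target PFS, event count or stopping rate, so everything below is illustration.

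**2. If only deaths count after stopping (closed form).** Assume exponential times.
- m = true median, f = fraction stopping before PD, M = median survival after stopping.
- λ = ln2/m (PD), c = λf/(1 − f) (stopping), μ = ln2/M (death after stopping).
- Reported curve: S(t) = e^(−(λ+c)t) + [c/(λ+c−μ)]·[e^(−μt) − e^(−(λ+c)t)]. Solve S(t) = 0.5.

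m = 11.1 months is the median *time to progression* that Section 3.3 cites for lenalidomide with pulsed dexamethasone. It serves only as a scale here. The values of f and M are assumptions.

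For m = 11.1, λ = 0.0624. With f = 0.33, c = 0.0624 × 0.33/0.67 = 0.0308. With M = 30, μ = 0.0231. The solution is t = 12.7.

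| f | M = 20 | M = 30 |
|---|---|---|
| 15% | 11.4 | 11.6 |
| 25% | 11.7 | 12.1 |
| 33% | 12.1 | 12.7 |

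The shift is 0.3 to 1.6 months on 11.1. The tail moves more: with f = 33%, S(24) is 28-31% against a true 0.5^(24/11.1) = 22%. For m = 6, f = 33% and M = 12-20, the median reads 6.6-7.0.

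**3. Does the direction depend on the rule? (simulation)** 400,000 patients per scenario, cut-off at 36 months. The medians of 6 and 12 months are the PFS range in Section 3.3. Median survival after progression is 18 − 6 = 12 and 36 − 12 = 24 months, from its overall survival range. The assumed PD hazard after stopping is 0.7, 1 or 2 times the on-treatment hazard. Kaplan-Meier medians, 6-month / 12-month case:

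| Stop without PD | Hazard ratio after stopping | True | Censored at stopping | Death or last contact used |
|---|---|---|---|---|
| 20% | 1 | 6.0 / 11.9 | 6.0 / 12.0 | 6.7 / 13.3 |
| 20% | 2 | 5.7 / 11.3 | 6.0 / 12.0 | 6.6 / 13.2 |
| 40% | 0.7 | 6.4 / 12.9 | 6.0 / 12.0 | 8.4 / 16.9 |
| 40% | 1 | 6.0 / 12.0 | 6.0 / 12.0 | 8.2 / 16.4 |
| 40% | 2 | 5.2 / 10.4 | 6.0 / 12.0 | 7.8 / 15.6 |

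(11.9 for 12.0 is simulation error.) Using deaths or last contact overstated the median in every scenario run. Censoring at stopping is unbiased at ratio 1, too high at ratio 2 and too low at ratio 0.7.

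**4. New therapy as a proxy event.** If every off-treatment progression led to new therapy within 0-3 months, the same simulation at ratio 1 gives 6.2 / 12.2 (20% stopping) and 6.6 / 12.5 (40%). That is much nearer the truth than deaths alone.

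**5. Against sampling error.** An approximate 95% interval for an 11.1-month exponential median, with every patient having an event, is 11.1·e^(±1.96/√n): 7.3-16.9 for n = 22 and 8.3-14.9 for n = 44.

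**The case against.** The strongest reply is that no section says patients are carried event-free to death. Silence on censoring is ambiguity, and censoring at the last disease assessment fits the text equally well. A full disease panel is due at discontinuation, and later therapy is collected, so much of what a sensible rule needs is already there. PFS is secondary, with no test or go/no-go rule. Patients with a DLT may stay on study at a reduced dose, which limits early stops. The illustrated shift in step 2 lies well inside the sampling error in step 5.

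Most of this stands, and it rules out two stronger readings. A reader might infer that PFS *is* overstated. The documents do not support that, because the direction depends on an unstated rule and on prognosis after stopping. A reader might also infer that the distortion is worst at the more toxic dose levels. Section 10.3 plans PFS only for the HTLD / HTLD-CKD group and the whole cohort, and the documents give no stopping rate by level.

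The reply does not remove the gap in the data. A censoring rule makes the estimate reproducible, but it does not supply the missing progressions or protect against informative stopping. A bias also does not shrink as patients are added, whereas sampling error does.

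**Conclusion.** The concern holds in this form: the schedule collects deaths but not progressions after discontinuation, so PFS as defined cannot be determined for patients who stop without PD. Bias is upward if deaths or last-contact dates are used, and can go either way under censoring at stopping.

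The illustrated size, about 11.4-12.7 months against 11.1, rests on exponential times, 15-33% stopping without PD, median survival of 20-30 months after stopping, and no off-treatment progression ever being counted. The 11.1 months is a time to progression from a different population: at amendment 7, patients in this trial had a median of 4.5 prior regimens and 88% were refractory to earlier lenalidomide. The actual size cannot be computed from the documents. The primary endpoint, first-cycle DLT, is unaffected. The change should be made, but the trial's main conclusion does not depend on it.

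**What to change.** 1. **Section 2 and Section 5.10:** add progression status and date, from local records, to the 3-monthly follow-up contact for patients who stopped without PD, until PD, death or 3 years from entry. Record the start date of any new anti-myeloma therapy at the same contact.
2. **Section 10.2.4:** state that patients without documented PD are censored at their last disease assessment and are not carried event-free on survival contact alone.
3. **Sensitivity analysis:** treat the start of new anti-myeloma therapy as an event.

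**Cost:** a short addition to the case report form at a contact that already takes place, and two or three sentences of analysis text. Sample size, eligibility and treatment do not change. The downside is that local progression dates are less exact than protocol assessments and may lack the two-assessment confirmation in Section 5.9.1, so they should be flagged as local. Patients who withdraw consent or are lost to follow-up will still have to be censored.
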